#### **10.1.2     *The Safety Evaluation of Combination Doses of BMS-986218 with Nivolumab (Part 1B)***

In the Safety Evaluation Combination Doses of BMS-986218 with Nivolumab (Part 1B), the starting dose of BMS-986218 will be at least 1 dose level lower than the highest monotherapy dose level of BMS-986218 demonstrating an acceptable safety profile, and will be administered in combination with nivolumab at the flat dose of 480 mg Q4W. Dose escalation and determination of MTD for the Safety Evaluation of Combination Doses of BMS-986218 with Nivolumab (Part 1B) will be guided by BLRM-copula with EWOC principle. Subsequent dose selection of the combination will be based on evaluating the recommendation from BLRM-copula and an overall assessment of all available safety and PK/pharmacodynamic data. Safety evaluation and tumor assessment will be performed Q8W (2 cycles). BLRM-copula will incorporate historical information from ipilimumab and nivolumab studies and the DLT information from the DLT period from both combination arms to estimate dose-toxicity surface, and will provide guidance for dose adjustment of either drug as needed.

While guided by the BLRM-copula, clinical assessment will take into consideration of the totality of available data including PK/pharmacodynamic from all treated participants in assigning a dose level for the next cohort of 3 participants. Six to 12 DLT-evaluable participants will be treated at

each combination dose. Additional participants may be treated at any dose combination below or at the BLRM-copula recommended dose combination for further evaluation of safety, PK, or pharmacodynamic parameters as required. A combination with a higher dose level of either drug may be considered if recommended per BLRM-copula, after consideration of all available safety, and PK/pharmacodynamic data. At no time will the dose of BMS-986218 in the Safety Evaluation of Combination Doses of BMS-986218 with Nivolumab (Part 1B) exceed the highest tolerated dose in the BMS-986218 Monotherapy Escalation (Part 1A). Up to approximately 84 DLT-evaluable participants will be enrolled in Part 1B.

#### **10.1.3    *The Randomized BMS-986218 Monotherapy Cohort Expansion in Cutaneous Melanoma (Part 2A)***

The primary purpose of the Randomized BMS-986218 Monotherapy Cohort Expansion in Cutaneous Melanoma (Part 2A) is to evaluate preliminary efficacy of BMS-986218 relative to ipilimumab 3 mg/kg. One hundred and thirty two response-evaluable participants will be randomized to BMS-986218 or ipilimumab evenly across study arms (eg, 33 participants to BMS-986218 at 7 mg Q4W; 33 participants to BMS-986218 at 20 mg Q4W; 33 participants to BMS-986218 at 70 mg Q4W; and 33 participants to ipilimumab) and stratified by the outcome (ie, progressed, relapsed) of previous anti-PD-1/PD-L1 immunotherapy. Additional response-evaluable participants may be randomized to further evaluate emerging data or subgroups of interest if needed but not to exceed 40 response-evaluable participants per arm. If additional participants are randomized, up to 160 response-evaluable participants (= 40 participants  $\times$  4 arms) may be randomized in Part 2A. The ORR of ipilimumab will serve as a control. With 33 treated participants in each BMS-986218 arm, the lower limit of the 1-sided 80% confidence interval for ORR difference from ipilimumab arm will be 12%, 7.3%, or 2.7%, assuming effect size of 20%, 15%, or 10%, respectively.

Although the above assumptions on the response rate were used for the purpose of sample size calculation, it should be noted that, to date, there are no anti-tumor response data available in this post anti-PD-1/PD-L1 population. The efficacy evaluation criteria may evolve by the time when the tumor data from this study are matured for evaluation.

#### **10.1.4    *The BMS-986218 Cohort Expansion - Monotherapy (Part 2B)***

The purpose of the BMS-986218 Cohort Expansion - Monotherapy (Part 2B) is to gather additional safety, tolerability, preliminary efficacy as monotherapy, PK, and pharmacodynamic information. However, the sample size calculation will be based on the ORR.

The preliminary efficacy of BMS-986218 as a monotherapy in solid tumors, including NSCLC, in participants who have received, and then progressed on, relapsed, or have been intolerant to, at least 2 standard systemic therapies with proven survival benefit according to their tumor types for metastatic and/or unresectable disease will be evaluated. Sixty-six response-evaluable participants will be randomized evenly across study arms (eg, 22 participants to BMS-986218 at 7 mg Q4W; 22 participants to BMS-986218 at 20 mg Q4W; and 22 participants to BMS-986218 at 70 mg Q4W). Additional response-evaluable participants may be randomized to further evaluate emerging data or subgroups of interest if needed but not to exceed a total of 40 response-evaluable

participants per arm. If additional participants are randomized, up to 120 response-evaluable participants (= 40 participants  $\times$  3 arms) may be randomized in Part 2B.

With 22 treated participants in each BMS-986218 arm, the lower limit of the 2-sided 80% Clopper Pearson confidence interval for ORR estimate will be 8.2%, 5.1%, or 2.4%, assuming ORR estimate size of 18%, 13.6%, or 9.1%, respectively.

#### **10.1.5    *The BMS-986218 Combination-Therapy Cohort Expansion in NSCLC (Part 2C)***

The purpose of the BMS-986218 Cohort Expansion - Combination Therapy (Part 2C) is to gather additional data including safety, tolerability, preliminary efficacy as combination therapy of BMS-986218 with nivolumab, in NSCLC. The sample size calculation will be based on the ORR.

Approximately 40 response-evaluable participants will be treated. Initial evaluation of efficacy signal (ORR) will be based on approximately the first 20 response-evaluable participants at a dose level, will be descriptive based on a point estimate and an 80% Clopper Pearson CI for ORR. In order for an 80% CI to exclude a 5.5% ORR (as reported for ipilimumab with nivolumab in similar population), at least 3 responders (15% ORR) will need to be observed in the first 20 participants evaluated at this dose. If 4 responders are observed (20% ORR), the 80% confidence interval will equal (9.0%, 36.1%). Based on the results of this initial evaluation, additional participants for a total of up to 40 participants may be treated at a dose level.

Furthermore, if 40 participants are evaluated at a dose level, there will be approximately 80% power to detect a difference between the null hypothesis assuming ORR of 5.5% and the alternative assuming ORR of 15%, based on a one group  $\chi^2$  test with a 0.10 one-sided significance alpha level. If more than one dose level is evaluated, up to 80 response-evaluable participants (= 40 participants  $\times$  2 arms) may be treated.

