- In the BMS-986218 Combination Therapy Cohort Expansion (Part 2C) in NSCLC, the preliminary efficacy and safety of BMS-986218 in combination with nivolumab will be assessed in participants with NSCLC who have progressed or relapsed after anti-PD-1/PD-L1 therapy. Participants must not have received prior anti-CTLA-4 therapy in the advanced or metastatic setting. One or more doses to be evaluated in Part 2C will be selected from the range of doses assessed as tolerable in Part 1B, and which do not exceed the MTD or highest dose administered that has cleared safety. These dose(s) will be selected based on the totality of available safety, tolerability, efficacy, PK and PD data. The evaluation of efficacy in Part 2C will initially occur at one or more dose levels starting with up to 20 participants at each dose level. Additional participants up to 40 at a dose level may be evaluated following initial signal assessment. In Part 2C, participants will be treated Q4W for up to 2 calendar years regardless of treatment delays.
- In the BMS-986218 Combination Therapy Cohort Expansion in MSS CRC (Part 2D), the preliminary efficacy and safety of BMS-986218 in combination with nivolumab will be assessed in participants with MSS CRC who have progressed or relapsed on at least 1 prior standard therapy. Participants must not have received prior anti-CTLA-4 therapy in the advanced or metastatic setting. The dose to be evaluated in Part 2D will be selected from the range of doses assessed as tolerable in Part 1B, and which do not exceed the MTD or highest dose administered that has cleared safety. The dose will be selected based on the totality of available safety, tolerability, efficacy, PK, and PD data. Regardless of whether or not RAS mutation status is known, all participants will be tested during screening for extended RAS (NRAS and KRAS) and BRAF mutation status. Results from this testing at screening is not required prior to receiving treatment on study. The RAS status evaluation will be conducted with the goal of enrolling approximately 20 participants each with either mutation or wild-type with respect to extended RAS status. The Sponsor may elect to prioritize enrollment of participants based on mutation status. In Part 2D, participants will be treated Q4W for up to 2 calendar years regardless of treatment delays.

The duration of the study will be approximately 5 years.

The study design schematic is presented in Figure 5.1-1.

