#### **10.3.9 *Interim Analyses***

Interim analyses will be performed for administrative purposes, internal decisions, or publications and they will be descriptive. No formal inferences requiring any adjustment to statistical significance level will be performed.

Preliminary efficacy may be assessed for Part 2 to determine an initial signal, and enrollment may be paused, prior to enrolling additional participants. Depending on enrollment rate and preliminary data there may not be a pause in enrollment. If an inadequate signal is detected from a preliminary analysis, then enrollment may be closed for that cohort.

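### Part 2C's stated power of about 80% is for a fixed 40 participants at a dose and leaves out the 20-participant look; the power of the staged plan depends on a continuation count that is not given

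*Combined protocol and SAP*

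**What the plan says.** Section 10.1.5 bases the Part 2C sample size on ORR. The first evaluation at a dose uses about 20 response-evaluable participants and is called descriptive: a point estimate with an 80% Clopper-Pearson interval. For that interval to exclude 5.5%, "at least 3 responders (15% ORR) will need to be observed in the first 20 participants evaluated at this dose". Depending on the result, "additional participants for a total of up to 40 participants may be treated at a dose level". The section then states that "if 40 participants are evaluated at a dose level, there will be approximately 80% power" for 15% against 5.5%, by a one-group chi-square test "with a 0.10 one-sided significance alpha level".

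Section 5.1 describes the same staging: "Additional participants up to 40 at a dose level may be evaluated following initial signal assessment". Section 10.3.9 adds: "If an inadequate signal is detected from a preliminary analysis, then enrollment may be closed for that cohort". It also says that enrolment may not pause for the look, and that interim analyses are descriptive with no adjustment of significance levels.

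No section gives a response count that decides continuation, or any operating characteristics for the sequence of 20 and then 40.

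**The concern.** The power figure belongs to a design in which all 40 participants are always enrolled. The plan instead describes a dose that normally goes from about 20 to 40 after an ORR look and that may be closed after it. A truly active dose can then fail in two ways: closure at 20, or too few responders at 40. The stated 80% counts only the second.

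At stake is the chance of dropping an active combination. Someone planning from Section 10.1.5 sees 80% and cannot tell how much of it the look uses up. The only count in the text is 3 of 20. If the team used it as the go criterion, the chance of closing a dose with the target ORR would be large, and it appears nowhere in the plan.

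**Working it through.** **Inputs, all from Section 10.1.5.** Null ORR p0 = 0.055; alternative p1 = 0.15; one-sided alpha 0.10; 40 at a dose; look at about 20, taken here as exactly 20 followed by 20.

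**1. The plan's own figure.** One-sample normal approximation:

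power = Φ{[(p1 − p0)√n − z₀.₉₀ √(p0(1 − p0))] / √(p1(1 − p1))}
= Φ{[0.095 × 6.325 − 1.2816 × 0.2280] / 0.3571} = Φ(0.864) = 80.6%.

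The stated 80% is reproduced.

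**2. Exact single-stage value.** Responders are whole numbers. At 4/40, z = (0.100 − 0.055)/√(0.055 × 0.945/40) = 1.248, below 1.282. At 5/40, z = 1.942. So 5 of 40 is the smallest rejecting count. Exactly, P(X ≥ 5 | 40, 0.15) = 73.7% and P(X ≥ 5 | 40, 0.055) = 6.7%. This step has nothing to do with the look; it is the baseline from which the cost of the look is measured.

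**3. The 3-of-20 count.** The lower 80% Clopper-Pearson limit is 5.64% at 3/20 and 2.69% at 2/20. The plan's count is right for the purpose it states.

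**4. Two-step power.** With continuation at r1 or more of 20 and success at 5 or more of 40:

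power = Σ over x ≥ r1 of P(X1 = x) × P(X2 ≥ 5 − x), with X1 and X2 each Bin(20, p).

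At p = 0.15 the upper tails P(X ≥ 1), …, P(X ≥ 5) for n = 20 are 0.9612, 0.8244, 0.5951, 0.3523 and 0.1702. The contributions are:

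- x ≥ 5: 0.1702
- x = 4: (0.3523 − 0.1702) × 0.9612 = 0.1751
- x = 3: (0.5951 − 0.3523) × 0.8244 = 0.2002; running total **0.545**
- x = 2: (0.8244 − 0.5951) × 0.5951 = 0.1365; running total **0.682**
- x = 1: (0.9612 − 0.8244) × 0.3523 = 0.0482; running total **0.730**
- x = 0: (1 − 0.9612) × 0.1702 = 0.0066; running total **0.737**

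The same sum at p = 0.055 uses tails 0.6774, 0.3019, 0.0943, 0.0218 and 0.0039.

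| Continue at | Closed at 20, ORR 15% | Closed at 20, ORR 5.5% | Power at 15% | False-positive rate at 5.5% |
|---|---|---|---|---|
| any count (no closure) | 0% | 0% | 73.7% | 6.7% |
| 1 or more of 20 | 3.9% | 32.3% | 73.0% | 6.6% |
| 2 or more of 20 | 17.6% | 69.8% | 68.2% | 5.8% |
| 3 or more of 20 | 40.5% | 90.6% | 54.5% | 3.8% |

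**5. Separating the two effects.** The move from 80.6% to 73.7% (6.9 points) comes from replacing the normal approximation by whole responders. The look itself costs 73.7 − 73.0 = 0.7 points, 73.7 − 68.2 = 5.5 points or 73.7 − 54.5 = 19.2 points, depending on the count.

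**6. Size of the look.** Because the look is at approximately 20, I varied it from 18 to 22 with the total held at 40. Under a 3-responder requirement, power runs from 48.3% to 59.8%.

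**The case against.** The strongest reply is that the sentence is correct on its own terms. It is conditional on 40 being evaluated, it names a one-group chi-square test, and that method gives 80.6%. Section 10.1.5 calls the look descriptive, and Section 10.3.9 makes closure optional and allows enrolment to run on. Section 5.2 plans for about 40 in Part 2C and counts more only if a second dose level is studied. Section 3.2.1 says no prospective hypotheses are formally evaluated, and Table 10.3.1-1 analyses ORR with an exact 95% interval, so success at 5 of 40 exists only in the sample-size argument.

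Most of this stands, and it limits the point. The 80% is not a slip in arithmetic, and no planned analysis is invalid. What does not follow is that the figure describes the plan: once responses in the first 20 influence who reaches 40, it does not.

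Two stronger readings are tempting and should be resisted.

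- A reader might infer that Part 2C has 54.5% power. The documents do not make 3 of 20 a continuation rule, so 54.5% is the lowest of the four scenarios tabulated, not the power of the design.
- A reader might infer that the 0.10 test should not be used after the look, because doses that reach 40 are selected. Given that 40 is reached, the chance of success at an ORR of 5.5% is 40.2% under a 3/20 rule (0.0379/0.0943), but 9.7% if only 0/20 closes a dose (0.0657/0.6774). The overall false-positive rate falls with every closure rule, from 6.7% to as low as 3.8%. A look that can only stop for futility does not inflate it.

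**Conclusion.** The point holds as a gap between the stated power and the staged plan. The 80% is a fixed-40 approximation. Its exact counterpart is 73.7%, and any closure based on the first 20 responses lowers that further: to 73.0%, 68.2% or 54.5% for continuation at 1, 2 or 3 of 20. None of these reaches 80%. The size of the shortfall cannot be settled from the documents, because the continuation count is not given.

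The figures assume a look at exactly 20, exactly 40 in total, success at 5 or more, and a closed dose counted as not successful. If the look never leads to closure, only the difference between approximate and exact power remains.

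This should be corrected, but it is not critical: no formal test is planned for Part 2C and overall false-positive control is not harmed.

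**What to change.** In Section 10.1.5:

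- Say whether 3 of 20 is a descriptive benchmark or the count that governs continuation.
- Name the futility count intended, if there is one.
- Replace the statement of approximately 80% power with the exact power, false-positive rate and probability of closure at 20 for that two-step procedure, taken from the table above. If 3 of 20 is the rule, that means stating 54.5% power, a 3.8% false-positive rate and 40.5% early closure at an ORR of 15%.
- If the look is wholly non-binding, give the exact single-stage figures (73.7% and 6.7%) as upper bounds, with the range for the possible counts.

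Sections 5.1 and 10.3.9 can then point to this text.

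The cost is wording and a less favourable stated power. No participants are needed beyond the 40 per dose already allowed. Choosing a lower continuation count would take more inactive doses to 40: at an ORR of 5.5%, 67.7% continue at 1 or more of 20, against 9.4% at 3 or more.

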It is anticipated that anti-CTLA-4-NF Ab (BMS-986218), administered as a single agent or in combination with anti-PD-1 Ab (nivolumab), will demonstrate adequate safety and tolerability, as well as a favorable benefit-risk profile, to support further clinical testing. No prospective hypotheses are being formally evaluated.

The scientific rationale for the study design is discussed in greater detail in [Section 5.4](#). Additional details are summarized in the BMS-986218 Investigator Brochure (IB).

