  - Part 2C - for the BMS-986218 Combination Therapy Cohort Expansion in NSCLC, approximately 40 response-evaluable participants will be treated. If more than one dose level is evaluated, additional participants (up to 40 response-evaluable participants per dose level) may be enrolled, up to 80 response-evaluable participants (= 40 participants  $\times$  2 arms).
  - Part 2D - for the BMS 986218 Combination Therapy Cohort Expansion in MSS CRC, approximately 40 response-evaluable participants will be treated, with the goal of treating approximately 20 participants each with either mutation or wild-type with respect to extended RAS status.

For additional details on sample size determination, see [Section 10.1](#).

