**Table 10.3.1-1: Efficacy - Statistical Analyses**

Endpoint	Statistical Analysis Methods
ORR is defined as the proportion of all treated participants whose BOR is either CR or PR by Investigator per RECIST v1.1 or per PCWG 3 criteria for prostate.  BOR for a participant will be assessed per RECIST v1.1 by Investigator, unless otherwise specified.	Estimate of ORR and corresponding 2-sided exact 95% CI using the Clopper-Pearson method by treatment for each tumor type.  For part 2A, estimate of difference in ORR between arms (using ipilimumab as reference) and corresponding 2-sided exact 95% CI using the Clopper-Pearson method by BMS treatment arms.
Median DOR  DOR for a participant with a BOR of CR or PR is defined as the time between the date of first response and the date of the first objectively documented tumor progression per RECIST v1.1 or per PCWG 3 criteria for prostate, or death, whichever occurs first.	Estimate by the Kaplan-Meier method and corresponding 2-sided 95% CI using Brookmeyer and Crowley methodology (using log-log transformation) by treatment for each tumor type.
PFSR at 24, 36, and 48 weeks  PFS for a participant is defined as the time from the first dosing date to the date of first objectively documented disease progression or death due to any cause, whichever occurs first.	Estimate PFSR by the Kaplan-Meier method and corresponding 2-sided 95% CI using Greenwood formula by treatment for each tumor type.  For part 2A, estimate difference in PFSR between arms (using ipilimumab as reference) by the Kaplan-Meier method and corresponding 2-sided 95% CI using Greenwood formula by BMS treatment arms.  Estimate median PFS by the Kaplan-Meier method and corresponding 2-sided 95% CI using Greenwood formula by treatment for each tumor type.

Abbreviations: BOR = best overall response; BMS = Bristol Myers Squibb; CI = confidence interval; CR = complete response; DOR = duration of response; ORR = objective response rate; PCWG 3 = Prostate Cancer Working Group; PFSR = progression-free survival rate; PR = partial response; RECIST = Response Evaluation Criteria in Solid Tumors.

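### Part 2C: the stated 80% power at 40 participants is a large-sample figure; the named test has exact power of 73.7% and exact alpha of 6.7%

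*Combined protocol and SAP*

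**What the plan says.** Section 10.1.5 bases the Part 2C sample size on the objective response rate (ORR). There are two steps at a dose level.

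- **First 20 response-evaluable participants.** The assessment is descriptive, using a point estimate and an 80% Clopper-Pearson interval. At least 3 responders are needed for that interval to exclude 5.5%, the rate the section cites for ipilimumab with nivolumab in a similar population.
- **Expansion.** Depending on that result, "additional participants for a total of up to 40 participants may be treated at a dose level". Section 5.2 repeats the limit: "additional participants (up to 40 response-evaluable participants per dose level) may be enrolled".

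For a dose level taken to the full 40, section 10.1.5 claims "approximately 80% power to detect a difference between the null hypothesis assuming ORR of 5.5% and the alternative assuming ORR of 15" percent. The method it names is a one-group chi-square "test with a 0.10 one-sided significance alpha level". It gives no responder count for n = 40.

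Two other places bear on the weight of this. Table 10.3.1-1 plans, for ORR, "Estimate of ORR and corresponding 2-sided exact 95% CI using the Clopper-Pearson method by treatment for each tumor type". Section 3.2.1 states: "No prospective hypotheses are being formally evaluated".

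**The concern.** With 40 participants and a null rate of 5.5%, about 2 responders are expected under the null (40 × 0.055 = 2.2). At counts this small the binomial distribution is coarse. One responder more or less moves the true error rates by many points, and a smooth normal formula can misstate them. The power sentence is also the only place in the section that leaves exact methods: the 20-participant look uses exact limits and names the responder count needed.

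This sentence is the only stated performance for a fully enrolled Part 2C dose level. If the true power is lower, a negative result at 40 participants will be credited with more sensitivity than it has. Without a stated count, a team could also take 4 of 40 (10%) as meeting the boundary, although the stated test does not reject there.

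**Working it through.** **Inputs, all from section 10.1.5:** n = 40; null ORR p0 = 0.055; alternative ORR p1 = 0.15; one-sided alpha 0.10, so z = 1.2816; one-group chi-square test, that is, a score test against p0.

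**1. Reproduce the plan's figure.**

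- Standard error under the null: √(0.055 × 0.945 / 40) = 0.03605
- Critical proportion: 0.055 + 1.2816 × 0.03605 = 0.1012, or 40 × 0.1012 = 4.05 responders
- Standard error under the alternative: √(0.15 × 0.85 / 40) = 0.05646
- Power: Φ((0.15 − 0.1012) / 0.05646) = Φ(0.864) = 80.6%

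This matches the stated figure. The same formula needs n = 38.9 for 80%, which rounds up to 39.

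**2. Apply the same test to whole responders.** z = (x/40 − 0.055) / 0.03605.

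| Responders x | z | Rejects (z ≥ 1.2816)? | P(X ≥ x) at ORR 5.5% | P(X ≥ x) at ORR 15% |
|---|---|---|---|---|
| 4 | 1.248 | no | 17.6% | 87.0% |
| 5 | 1.942 | yes | 6.7% | 73.7% |

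The rule is 5 or more of 40. Exact alpha is 6.7%, exact power is 73.7%, and the miss rate is 100 − 73.7 = 26.3%. Power reaches 80.3% at a true ORR of 16.3%.

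**3. Compare with the interval the section itself uses.** The 80% Clopper-Pearson limits at n = 40 are:

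- 4/40: 4.4% to 19.0%, which does not exclude 5.5%
- 5/40: 6.2% to 22.0%, which excludes 5.5%

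The cutoff is the same. The section's own 20-participant figures reproduce by this method: 3/20 has a lower limit of 5.6%, and 4/20 gives 9.0% to 36.1%.

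**4. See whether a nearby n rescues the claim.** For the same chi-square test:

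| n | Cutoff | Exact alpha | Exact power at 15% |
|---|---|---|---|
| 36 | 4 | 13.4% | 80.9% |
| 39 | 4 | 16.5% | 85.7% |
| 40 | 5 | 6.7% | 73.7% |
| 43 | 5 | 8.6% | 79.3% |
| 44 | 5 | 9.3% | 81.0% |

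Just below 40 the power exceeds 80%, but only because the exact alpha is above 0.10. Taking the smallest cutoff with exact alpha of at most 10% at each n, the highest power for any n from 5 to 40 is 73.7%. The first n with power of at least 80% is 44.

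**The case against.** The strongest reply is that nothing has been miscalculated. The section names an asymptotic test, says the power is approximate, and the standard formula gives 80.6%. The value 40 is also an unlucky one, because the boundary falls just past a whole number; the same test at 39 has exact power of 85.7%. The section speaks of approximately 40 participants, section 7.4 bars replacement after dosing in Part 2, and the final analysis uses all treated participants, so the realised denominator may not be 40. Finally, Table 10.3.1-1 schedules no test against 5.5%, and the study evaluates no formal hypotheses.

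Much of this stands. The 80% is a correct use of an approximation, and no confirmatory conclusion depends on it. It does not rescue the sentence. A miss rate of 26% against 20% is more than rounding, and the better power at 36 to 39 comes with a true alpha of 13.4% to 16.5% against the stated 0.10. The plan cannot have both stated properties within its cap.

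Two cautions about the replacement figure are also fair.

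- **It is a single-stage figure.** Expansion depends on the first 20, and section 10.3.9 allows a cohort to close for inadequate signal. No gate is fixed. If one assumes expansion requires at least 1, 2 or 3 responders in the first 20, the chance at ORR 15% of both expanding and reaching 5 of 40 is 73.0%, 68.2% or 54.5%.
- **It is tied to the 80% interval.** Under the 95% Clopper-Pearson interval in Table 10.3.1-1, the lower limit at 5/40 is 4.2%, and 6/40 (5.7%) is needed to exclude 5.5%.

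**Conclusion.** The concern holds. The stated test at 40 participants rejects only at 5 or more responders (12.5%). Its exact power at ORR 15% is 73.7%, about 6 points below the stated 80%, and its exact alpha is 6.7% rather than 10%. These figures assume independent binomial responses, exactly 40 participants in the denominator, and a single stage; stopping after the first 20 can only lower the power. The consequence is limited to how a dose level with fewer than 5 responders is interpreted. The sentence should be corrected, but the design need not change.

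**What to change.** Replace the power sentence in section 10.1.5 with:

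> If 40 participants are evaluated at a dose level, at least 5 responders (12.5%) are needed to exclude an ORR of 5.5% (80% Clopper-Pearson CI 6.2% to 22.0%). The exact one-sided alpha is 6.7%, and the exact power is about 74% at ORR 15% and about 80% at ORR 16.3%.

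The sponsor may add that the power is a single-stage figure and takes no account of stopping after the first 20. It would also help to report the 80% Clopper-Pearson interval for Part 2C beside the 95% interval in Table 10.3.1-1, so that the comparison with 5.5% uses the planning interval.

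The main correction is wording only: no extra participants and no change to the analysis. Its one cost is a less favourable stated power, 74% in place of 80%. Keeping 80% power with exact alpha of at most 10% would instead require 44 participants and a change to the cap of 40; that is not needed for signal-finding.
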